The VA Maryland Health Care System (VAMHCS) desires to test secure messaging in My HealtheVet (MHV) for communication with research participants in the IRB approved (HP-60526), VA Funded Stroke Rehabilitation Trial "Translating Intensive Arm Rehabilitation in Stroke to a Telerehabilitation Format" aka TeleBATRAC. We are working collaboratively with the Veterans and Consumers Health Informatics Office, VHA Office of Analytics, VA Office of Connected Care, and the Office of Research and Development. We aim to assess potential and specific concerns articulated by our national collaborations, which have included: Secure Messaging triage team naming conventions, procedures for the registration, authentication and secure messaging Opt-In for veteran and non-veteran research participants, association with the study triage team, training of study participants and research triage team recipients, informed consent (to include visibility of secure messaging research communication and data to clinical management teams), management of messages and retention of data, ease of message reassignment, the identification of unintended consequences, and development and collection of data and information to inform future VA research policy and guidance.

MyHealtheVet Secure Messaging Pilot Aims and Hypotheses

Aim 1: To develop and pilot test a Home-based stroke rehabilitation program using the MHV patient portal and secure messaging as the communication delivery system.

Aim 2: To assess for differences in eHealth literacy and self-efficacy between the Delayed Entry Usual Care and the Home-based rehabilitation group using MHV secure messaging.

Hypothesis 1: Home-based MHV stroke survivor & caregivers' intervention group Web-Based Learning Self-Efficacy Scores will meet or exceed the Delayed Entry Usual Care group.

Hypothesis 2: Home-based MHV stroke survivors and caregivers' intervention group eHEALS Health Literacy Scale will meet or exceed the Delayed Entry Usual Care group scores.

Aim 3: Determine efficacy of the two (2) one-hour structured MHV training on stroke survivors and caregivers Web-Based Learning Self-Efficacy Scores (WBLSES) and eHEALS scales.

Hypothesis 1: Home-based MHV stroke survivors and caregivers' intervention group WBLSES will exceed the baseline scores at the end of the clinical trial demonstrating improved comfort and skill in using the MHV patient portal.

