evaluations in the same time intervals as those receiving active interventions and weekly phone calls to record general activity level. During this time frame, this group may participate in the MyHealtheVet Secure Messaging Pilot to receive the pilot pre and post evaluations and interviews. Every effort will be made for MyHealtheVet Secure Messaging Pilot appointments to be coordinated with the Primary Study appointments to avoid undue travel. After serving as a control, this group will be entered into their delayed active intervention group of either lab-based BATRAC + TTT training, or Lab-based Robot+ TTT.

3 * Describe the relevant prior experience and gaps in current knowledge. Describe any relevant preliminary data:

Expanding the continuum of care to home has significant barriers due to limited opportunity for education, and limited access to rehabilitation professionals which may lead to poor adherence to the rehabilitation program. These barriers can potentially be addressed using modern telemedicine technologies already established at the VA for aspects of healthcare management on their MyHealtheVet website. This will act as a resource for support and involvement of the caregiver in the exercise program. The benefit of family involvement in recovery of upper extremity motor function has yet to be fully investigated. A qualitative study by Galvin et al. found that family members of stroke survivors were willing to participate in unsupervised exercises but indicated a lack of confidence in assisting with the exercises as one of the barriers (Galvin 2009). Additionally, a recent study by Harris et al. found caregiver involvement to be a significant determining factor in improved arm function over and above initial severity of motor impairment and exercise intensity (Harris 2010). Although there are a growing number of studies evaluating various telerehabilitation interventions in stroke, reports using this potentially promising technology for comprehensive home-based upper limb rehabilitation are limited.

In this project, we seek to objectively assess the impact of a comprehensive patient-centered, home-based upper limb telerehabilitation program augmented with an VA approved asynchronous on-line communication website. Results of the study will provide information on the use of this modern technology to improve care in Veterans with stroke related upper extremity neuromuscular impairments.

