Robotic Bimanual Coordination Evaluation: The KinArm robot, a clinical arm robot designed to assess post-stroke sensorimotor deficits and quantify bilateral arm movements will be used to examine arm kinesthesia and bimanual impairment. The robot evaluation will be performed in a seated position with each arm supported by the robot exoskeleton. Participants will be prompted by a visual target or be moved by the robot to mirror-match arm positions within a horizontal plane of motion. The robot will record and store all movement data. Safety will be ensured with a study staff member present at all times. The robot also has an emergency stop system built in for quick termination of any testing if necessary. This evaluation will occur one time at baseline and one time post-training. Time to administer 30-40 minutes.

Telerehabilitation Study Satisfaction Surveys (Home-based Tele rehabilitation Group and Clinic-based Group) :

Home-based Telerehabilitation Group: This is a 17 question survey of participant satisfaction with the telerehabilitation format. 10 questions use a 5-point Likert scale to address ease of use, convenience, understanding of information provided and general satisfaction. There are 6 open-ended questions for participant comments. Time to administer is approximately 10 minutes.

Clinic-based Group: This is an 12 question survey of participant satisfaction with the clinic-based training format. 5 questions use a 5-point Likert scale to address ease of use, convenience, understanding of information provided and general satisfaction. There are 6 open-ended questions for participant comments. Time to administer is approximately 5-10 minutes.

Home Activity Questionnaire (for Delayed-Entry group only): This is a 10 question survey of activities completed in the week that incorporated the affected arm. Also to record general household activities and community outings. Time to administer is approximately 5 minutes.

MyHealtheVet Training (for the home group only): Training and education about registration and use of MyHealtheVet secure messaging to communicate with the study team will be completed if randomized to the home group. This will take approximately 15 minutes.

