1. eHealth Literacy Scale (eHeals): This is an 8-item questionnaire that measures your perceived ability and comfort using information technology for health. It will be used to gain an understanding of your electronic health literacy at the beginning and again at the end of the study. It should take approximately 5 minutes to complete.

2. Web-Based Learning Self-Efficacy Scale (WBLSES): This is an 8 to 12 item questionnaire used to rate your confidence using electronic tools for web-based online learning. Questions ask you to rate your opinion the MyHealtheVet instructions used, availability of assistance, amount of time available to complete the items, encouragement, physical conditions and computer navigation methods. It will be given at the outset of the study and again at the end of the study. It should take approximately 5 minutes to complete.

3. Montreal Cognitive Assessment (MoCA): The Montreal Cognitive Assessment is a 30-point screening instrument that has been validated to detect mild cognitive impairments or deficits in attention, memory, learning and visuospatial functions that may be due to neurological deficits consistent with stroke. The MoCA will be used to gain a general baseline of study participant's cognitive functioning and should take no more than 20 minutes to complete.

4. Interview: Post-training interviews will be completed after you receive instruction in using the MHV website for access to the secure messaging portal and mail group. This interview will be completed after your initial instruction and at any follow-up training. Questions will focus on your experience with the training and confidence using the site.

Qualitative Study Additional Procedures

1. Background Questionnaire: There are two versions of the background questionnaire; one designed for a study participant and one for staff and lab personnel employed by the VA Maryland Health Care System or University of Maryland. This is an 8-12 item questionnaire used to gather the study participants', staffs' or lab personnel's prior experience with the My HealtheVet patient portal and its tools prior to using it and or being involved in the design and implementation in the My HealtheVet Secure Messaging Pilot Study. It should take approximately 5 minutes to complete.

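### Pilot Aim 2 Hypothesis 1 compares a self-efficacy total that partly rates MyHealtheVet instruction controls have not had, and neither Aim 2 scale has a common second reading

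*Combined protocol and SAP*

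**What the plan says.** The pilot aims are in Justification, Objective, & Research Design, item 1. Aim 2 has two hypotheses. For the WBLSES, the home "intervention group Web-Based Learning Self-Efficacy Scores will meet or exceed the Delayed Entry Usual Care group". For the eHealth literacy scale (eHEALS), the home "intervention group eHEALS Health Literacy Scale will meet or exceed the Delayed Entry Usual Care group scores".

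Study Procedures, item 1 (pilot questionnaires) describes the WBLSES in two ways. It is "used to rate your confidence using electronic tools for web-based online learning". Then: "Questions ask you to rate your opinion the MyHealtheVet instructions used, availability of assistance, amount of time available to complete the items", followed by encouragement, physical conditions and navigation methods. The eHEALS "measures your perceived ability and comfort using information technology for health" and is described without reference to MyHealtheVet (MHV) instruction.

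On exposure, Study Procedures carries the entry "MyHealtheVet Training (for the home group only". The Delayed Entry Usual Care paragraph of the design section (item 2) says that controls get no study intervention in the control period beyond evaluations and weekly calls.

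On timing, the eHEALS is given "at the beginning and again at the end of the study", and the WBLSES entry follows the same rule. The Delayed Entry paragraph, speaking of the control period, says "this group may participate in the MyHealtheVet Secure Messaging Pilot to receive the pilot pre and post evaluations and interviews".

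**The concern.** A between-group comparison of a questionnaire score needs items that mean the same thing in both groups and a reading at the same point. Neither is secured here.

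If part of the WBLSES total rates instruction that one group had and the other did not, a difference in totals mixes receipt of instruction with self-efficacy. The plan does not say how a control should answer an item about instruction not received, or how a blank would be scored. The size and direction of the distortion are therefore unknown.

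The timing problem affects both scales. If controls are read in their control period and home participants at the end of the study, group is confounded with time since randomization. If both are read at the end of the study, the controls have by then had active training and are no longer usual care.

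The pilot is meant to inform future VA policy on secure messaging in research, so an unclear result would matter there. The parent trial and its Wolf Motor Function Test outcome are not affected.

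**Working it through.** The documents give no sample size, margin, test or power for pilot Aim 2, and Sample Size and Data Analysis contains no pilot analysis. There is no pilot figure to reproduce. The check is one of content and of schedule.

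**Content, at the second reading**

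- *General confidence with web-based tools (WBLSES)*: answerable in both groups.
- *Opinion of the MHV instructions used (WBLSES)*: answerable by trained home participants. Controls in their control period have had no such instruction from the study.
- *Assistance, time, encouragement, physical conditions, navigation (WBLSES)*: depends on whether the item refers to the MHV training or to web use in general. The questionnaire text is not available here.
- *eHEALS*: answerable in both groups as described.

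The WBLSES is said to have 8 to 12 items. How many concern MHV instruction is not stated, so the affected share of the total cannot be calculated.

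**Schedule**

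Inputs, from the design section (item 2) and Study Procedures (item 3): training 6 weeks, at most 9; retention period 8 weeks; control period 6 weeks; baseline phase 4 weeks. Weeks below count from randomization, assuming that each phase follows directly on the last.

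The plan's own totals reproduce:

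- Design section: 9 + 8 = 17 weeks (immediate entry) and 6 + 9 + 8 = 23 weeks (delayed entry).
- Study Procedures, with baseline: 4 + 9 + 8 = 21 and 4 + 6 + 9 + 8 = 27 weeks.

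End of study therefore falls at:

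- Home: 6 + 8 = 14 to 9 + 8 = 17 weeks.
- Controls: 6 + 6 + 8 = 20 to 6 + 9 + 8 = 23 weeks.

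Three readings of the text follow.

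1. *Controls read in the control period, home at end of study.* Controls week 6, home weeks 14 to 17. Gap: 14 − 6 = 8 to 17 − 6 = 11 weeks.
2. *Both read at end of study.* At equal training length the gap is 20 − 14 = 23 − 17 = 6 weeks, and controls have completed active training. Sample Size and Data Analysis adds 11 of the 22 controls to each active arm, so 11/22 = 50% would have been in the home arm. The Delayed Entry paragraph instead lists only two lab-based options, which gives 0%.
3. *Home read at end of training.* Home weeks 6 to 9, controls week 6. Gap: 0 to 3 weeks. No section states this timing for the pilot.

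**The case against.** The strongest reply is that the WBLSES is introduced as a general confidence scale and is given at the outset, before the intervention, in both groups. The plan evidently expects people without study instruction to answer it. MHV is also an existing clinical portal that some controls may already use, and the Interviews section plans interviews with delayed-entry participants about it. In addition, the contrast between a group using MHV and an untrained group is what Aim 2 sets out to examine. Finally, the Research Protocol and Surveys/Questionnaires pages list a separate pilot protocol and the questionnaire itself, which may settle item wording and visit timing.

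Much of this stands. It limits the content point to the items on MHV instruction and keeps the general items usable. It does not rescue the total score: prior use of the portal is not the study instruction being rated, and an intended difference in exposure is no reason to score an item that only one group can answer.

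Stronger readings are tempting but not supported:

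- *That controls never receive the instruction.* This holds for the control period. Elsewhere the design section, the sample-size section and the recruitment text allow later entry to the home arm.
- *That Aim 2 cannot be validly tested.* The eHEALS hypothesis has no content problem, and a narrowed WBLSES comparison remains possible.
- *That the plan schedules an 8 to 11 week mismatch.* That gap is the literal result of sections that have not been reconciled. No section gives a week for the Aim 2 comparison.
- *That 11 of 22 pilot controls would be portal-trained.* That is a parent-trial count. The pilot is opt-in and its size is not stated. At most the proportion of one half carries over, and under the Delayed Entry paragraph it is zero.
- *That missing or guessed control answers would favour the home group.* No scoring rule is given, so the direction is unknown.

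**Conclusion.** The point holds in limited form and is minor in weight. As described, the WBLSES total in Aim 2 Hypothesis 1 is not like-for-like at the second reading, because some items rate MHV instruction that controls have not received from the study in their control period. Items on general confidence remain comparable. Separately, neither Aim 2 scale has a common second reading. Depending on which section governs, the groups are read 8 to 11 weeks apart, or about 6 weeks apart with controls already through active training (half or none of them in the home arm, depending on the section).

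This rests on the questionnaire content as summarized in Study Procedures, on end of study meaning the retention visit, and on phases following each other without delay. The pilot protocol and the questionnaire could change it.

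**What to change.** 1. For the Aim 2 between-group comparison, read eHEALS and WBLSES in both groups at the end of the first 6-week period, before controls start active training. For home participants this is the existing end-of-training visit. Because training may run to week 9, state the allowed window; up to 3 weeks' difference can remain.
2. List the WBLSES items answerable without MHV instruction, compare only those between groups, and report the instruction items descriptively in the home group.
3. Keep the end-of-trial reading for within-home change (Aims 3 and 4).
4. Reconcile the design section, its Delayed Entry paragraph and the sample-size section on which arms controls enter after the control period.
5. If the pilot protocol or questionnaire already settles item wording or timing, align the aims, the Delayed Entry paragraph and the questionnaire descriptions with it.

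The cost is protocol wording and one 5-minute form per scale (2 × 5 = 10 minutes) for home pilot participants and caregivers at a visit already planned. Hypothesis 1 becomes narrower but need not be dropped.

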Hypothesis 2: Home-based MHV stroke survivors and caregivers intervention group eHEALS Health Literacy Scale will exceed the baseline scores at the end of the clinical trial demonstrating improved comfort and skill in using secure messaging for health care management.

Aim 4: Determine efficacy of stroke survivors and caregivers use of the MHV patient portal and Secure Messaging for communication with research team.

Hypothesis 1: Home-Based MHV stroke survivors and caregivers intervention group WBLSES and eHeals literacy scores will increase from baseline demonstrating improved comfort and skill in the use of the MHV patient portal and secure messaging for health care management.

Hypothesis 2: Home-Based MHV stroke survivors and caregivers secure messaging volume will increase over the 18 week period of the study demonstrating improved comfort and skill in the use of secure messaging and enhanced self-efficacy for self-regulated stroke rehabilitation.

2 * Discuss the research design including but not limited to such issues as: probability of group assignment, potential for subject to be randomized to placebo group, use of control subjects, etc.:

This is a longitudinal, single blind, randomized controlled trial with three parallel 6 week intervention arms conducted over a three-year time period :

1) Home-based BATRAC Telerehab (HBT) + TTT, 2) Lab-based BATRAC (LBB) + TTT, and 3) Delayed Entry Usual Care group that will serve as a control for the initial six weeks of enrollment and NOT receive an active study intervention before randomizing to one of the two active interventions. This strategy will ease recruitment needs, reduce attrition from the delayed entry group, and spread the training schedule more equally across the three years. In order to have a better understanding of general function in the chronic stage of recovery for this moderately to severely impaired cohort we will conduct weekly phone calls to the delayed entry group during the 6 week control period and record general activity (household or community) and monitor amount and intensity of arm use. After serving as a control, this group will be randomized to one of the two active interventions.

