Our most recent preliminary robot assisted arm training study addressing moderate to severe chronic upper extremity deficits suggested intensive reaching combined with a brief period of task specific training or transition to task training (TTT) leads to greater gains than robot-assisted training alone. An earlier change was seen in the course of the intervention with an overall improvement in time to complete tasks for the Wolf Motor Function Test (WMFT). The mean WMFT time change was 9.4 seconds (\pm SD 10.3) from baseline. This magnitude of change is similar to that reported in the literature for the EXCITE constraint-induced movement trial (Wolf 2006) and representative of a clinically important difference (Lin 2009). Additionally, an analysis of participants' self-reported hand function using the Stroke Impact Scale (SIS) hand domain showed significant within group changes not seen in the robot only group as well as significant between group differences.

BATRAC Outcomes: There are several published laboratory studies of using BATRAC in chronic stroke with patients with a range of severity consistent with our proposed population. All but one have used the proposed scheduling protocol and have demonstrated significant immediate pre-post changes in the primary variable of WMFT timing. The mean improvement from these studies were 4.0 (Whitall 2000), 3.3 (Luft 2004), and 2.6 seconds (Whitall 2011). All of these exceed the clinically important difference of 1.5 to 2 seconds derived by Lin et al for chronic stroke patients. Where retention was assessed, the gains did not disappear. Even the one modified study schedule (8 sessions x 2.25 hours over 2 weeks), by a different research group, demonstrated a significant increase of paretic arm use. Recent submitted data, where we have been more aggressive in progressing parameters have shown an improvement of 7.4 ± 7.6 seconds ($p=.004$) on the WMFT time.

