2. Interview: a) A face-to-face semi-structured interview will be conducted after completion of the My HealtheVet Secure Messaging Pilot and Qualitative Study for first time participants, and after for returning study participants enrolling in the Qualitative Study focusing on your overall experiences and perspectives on My HealtheVet use; b) staff, students, and laboratory personnel enrolled in the Qualitative Study will complete a face-to-face semi-structured interview examining their experiences and perspectives of the four features of the My HealtheVet patient portal and Secure Messaging. The interview is expected to take approximately one-hour to complete.

3. Focus Group: A face-to-face semi-structured focus group may be conducted with VA Maryland Health Care System and University of Maryland staff, students and laboratory personnel, if the option is elected by members of this group. The focus group interview process will be used to elicit observations and experiences that may only come to light as a result of sharing experiences in an open forum. The focus group is expected to take approximately one-hour to complete.

2 * Describe all procedures already being performed for diagnostic or treatment purposes (if not applicable to the study, enter "N/A"):

N/A

3 * Describe the duration of an individual participant's participation in the study:

Each patient will be enrolled in the study and seen for baseline evaluations in the 1st month followed by 6 weeks of randomized intervention 3 times/week for 18 training sessions. This training time will be spread over a maximum of 9 weeks to allow for missed visits due to transportation/weather or minor illness. Participants will be asked to return for a retention follow-up after 8 weeks of no training. Maximal study time commitment will be 21 weeks.

Participants initially randomized to the 6 weeks delayed entry group will have a potential maximum study commitment of 27 weeks (4 week baseline + 6 week delay + max 9 weeks of intervention + 8 week retention).

4 * Describe the amount of time it will take to complete the entire study:

This study will be 3 years in length.

5 * Describe any additional participant requirements:

N/A

Sample Size and Data Analysis

If you uploaded a separate research protocol document in the 'Research Protocol' page, cite the applicable section and page numbers from that document in the answer boxes below.

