Co-I/Biostatistician [name] will actively participate in planning and conducting data analysis. Descriptive analyses including constructing graphical displays of the data and frequency distributions will be performed. Non-normally distributed data will be transformed to normality or categorized, whichever is more appropriate. Robust or nonparametric analysis will be performed as required. Patient characteristics (including age, race, gender, time since stroke, pre-stroke handedness), impairment severity (baseline FM score) as well as comorbidities (cardiac history, and diabetes) will be compared between intervention groups.

Aim #1 Analysis of Home-based BATRAC Telerehabilitation + TTT

The goal of this aim is to determine the efficacy of home-based BATRAC compared to usual customary stroke care for Veterans with chronic upper extremity stroke deficits. The primary outcome will be the change in the WMFT score from baseline to completion of the six-week intervention. We will use intention-to-treat (ITT) analysis and include all subjects who are randomized in the analysis. The primary analysis will be a two sample T test with a significance level of 0.025.

Alternative analysis for Aim 1: As an alternative analysis, we will compare our primary outcome measures adjusting for imbalanced baseline covariates, by using a linear regression model. As secondary analyses, we will examine outcome measures on multiple levels of the International Classification of Function including impairment, activity level and participation to provide an extensive examination of abilities. To assess the time trend of WMFT score in the home-based BATRAC group and in the usual care group, we will use linear mixed models that are similar to 2-way ANOVA with treatment group (2) X time (2) with repeated measures on the last factor. The independent variables will include time at which the outcome was measured i.e., pre (average of 3 time points), post training (~6 weeks) and after retention (~14 weeks), treatment group (Home-based BATRAC Telerehab + TTT, and Usual Care), baseline FM group (the stratification variable), and the possible interaction terms between treatment group and time and possible interaction terms between treatment group and baseline FM group. If the interaction terms are not statistically significant, they will be removed from the model. We can also include imbalanced baseline covariates into the linear mixed models.

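### The secondary Aim 1 mixed model lists a ~14-week retention level for home training versus Usual Care, but the design yields no usual-care observations after week 6

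*Combined protocol and SAP*

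**What the plan says.** The alternative analysis for Aim 1 (Sample Size and Data Analysis, item 2) describes linear mixed models for the WMFT time trend in the home and usual-care groups. The layout is given as "treatment group (2) X time (2) with repeated measures on the last factor". The time variable is then listed as "pre (average of 3 time points), post training (~6 weeks) and after retention (~14 weeks". The last time level and the group variable stand side by side in that list: "after retention (~14 weeks), treatment group (Home-based BATRAC Telerehab + TTT, and Usual Care". Interactions of group with time and with the Fugl-Meyer stratum may be included, and are dropped if not significant.

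Under Justification, Objective, & Research Design, item 2, the delayed-entry arm is to be a "control for the initial six weeks of enrollment and NOT receive an active study intervention before randomizing to one of the two active interventions". Its maximum commitment is set out under Study Procedures, item 3, as "4 week baseline + 6 week delay + max 9 weeks of intervention + 8 week retention". Evaluations are placed at baseline, at training completion and at a retention visit 8 weeks later. The Aim 2 power calculation counts the delayed-entry participants as active: 22 plus 11 in each active group.

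The primary Aim 1 analysis is separate. It is a two-sample t test on WMFT change from baseline to the end of the six-week intervention.

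**The concern.** The model names a comparator at a time when the design no longer has one. By ~14 weeks, delayed-entry participants who follow the plan have finished active training or are still in it. The analysis paragraph does not say what happens to their scores after crossover. An analyst would have to choose between two courses: keep them under their original label, or leave the retention cell for Usual Care empty. On the first, the retention contrast is contaminated, and a durable home benefit could look as if it had faded. On the second, there is no retention contrast to report. This is the only Aim 1 model that addresses retention, so the choice should not be left until the data are in hand.

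**Working it through.** **1. The plan's own figure.** Inputs from Sample Size and Data Analysis, item 1: mean change 0 s (usual care) and 7.4 s (home), SD 7.6, two-sided alpha 0.025, 22 per group.

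- Standard error = 7.6 × √(2/22) = 2.29 s.
- Noncentrality = 7.4 / 2.29 = 3.23, with 42 degrees of freedom and critical t = 2.32.
- Power by the noncentral t = 81.3%. The stated 22 per group for 80% is reproduced.

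This calculation concerns the ~6-week change, when the delayed-entry group is still untreated. Nothing below alters it.

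**2. Timeline, in weeks after the baseline phase.** Training takes 6 weeks (maximum 9), the delay is 6 weeks, and retention is 8 weeks after training.

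| Group | End of control | Post-training | Retention |
|---|---|---|---|
| Home (immediate) | – | 6 (max 9) | 6 + 8 = 14 (max 9 + 8 = 17) |
| Delayed entry | 6 | 6 + 6 = 12 (max 6 + 9 = 15) | 12 + 8 = 20 (max 15 + 8 = 23) |

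The maxima of 17 and 23 weeks agree with those stated under Justification, item 2. Planned usual-care observations at ~14 weeks: 0. The two delayed-entry visits after week 6 both follow active training, and the retention visit is also on a later clock.

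**3. What a post-crossover score would do to the contrast.** Assumptions: home gains are fully retained, in line with the plan's summary of earlier BATRAC studies ("Where retention was assessed, the gains did not disappear"); controls have realised a fraction f of the 7.4 s gain; n = 22 per group, SD 7.6 and two-sided alpha 0.025 carry over. The contrast is 7.4 × (1 − f). The documents do not give f, so a range is shown.

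| f | Contrast at ~14 weeks (s) | Power |
|---|---|---|
| 0 | 7.40 | 81% |
| 0.25 | 5.55 | 54% |
| 0.5 | 3.70 | 25% |
| 0.75 | 1.85 | 7% |
| 1 | 0 | 2.5% (the alpha level) |

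**4. Would the ~6-week contrast be harmed too?** Only if the group-by-time term is dropped. Assume equal correlation between times and a 0.05 test. The within-person variance is then 7.6²/2 = 28.88.

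- f = 1: group differences at the three times are 0, 7.4, 0, with mean 2.47 and sum of squared deviations 36.5. Noncentrality = (22/2) × 36.5 / 28.88 = 13.9 on 2 and 84 degrees of freedom; the interaction is significant about 92% of the time.
- f = 0.5: differences are 0, 7.4, 3.7, with mean 3.7 and sum of squared deviations 27.4. Noncentrality = 10.4; about 82%.

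In most repetitions the interaction would stay in the model and the ~6-week contrast would remain separately estimated.

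**The case against.** The strongest reply is that the plan never says post-crossover scores will be coded as Usual Care. The two-level time layout may mean that only baseline and ~6 weeks were intended, with the retention level filled by the home arm alone. No delayed-entry visit is scheduled at week 14. The sentence describes a secondary analysis, and neither main hypothesis claims durability against usual care.

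Much of this stands. A reader might infer that the plan commits to comparing trained with trained participants under a Usual Care label. The text does not go that far; it leaves the handling open. But the two-level layout does not settle the matter, because the next sentence lists three times for the same two groups. The delayed-entry paragraph also promises evaluations at the same intervals as the active arms, which invites a retention row.

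Three other stronger readings are not supported:

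- A reader might average weeks 6 and 14 at full control gain, (7.4 + 0)/2 = 3.7 s, and say that the model halves the effect. That average is not a quantity the model targets. With the interaction removed, the group term would also average over baseline (about 2.5 s for 0, 7.4, 0), so part of that dilution has nothing to do with crossover.
- A reader might say that the week-14 contrast will be zero. That needs controls to have realised the whole gain and home participants to have kept all of theirs, although some controls may still be training then.
- A reader might assume that every control moves to home or lab BATRAC. The design overview and the recruitment hand-out say so, but the delayed-entry paragraph closing Justification, item 2, names lab BATRAC or a lab robot. These places must be reconciled. Under either version the controls are in active training.

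**Conclusion.** The point holds for the secondary Aim 1 mixed model. At ~14 weeks there is no usual-care comparator by design: the retention contrast is either contaminated by crossover or not estimable. The statement of two time levels alongside three listed times is an inconsistency in its own right. The possible distortion runs from none to the full 7.4 s, depending on how much of the gain controls have realised (an assumption) and on home gains being retained. Controls who withdraw before crossover would not supply a randomised comparator.

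The primary ~6-week t test keeps a valid control, and its 22 per group is reproduced. This should be fixed before analysis, but it does not threaten the main result.

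**What to change.** Rewrite the mixed-model paragraph to say that:

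- the home versus usual-care model uses baseline and ~6 weeks only, which is the 2 × 2 layout already stated;
- delayed-entry WMFT scores obtained after the second randomisation are not entered as Usual Care in any analysis;
- ~14-week retention is analysed as change within the home group and as home versus lab;
- the trial provides no randomised retention comparison against usual care.

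Separately, reconcile the passages on which active training follows the delay, so that later delayed-entry data carry an unambiguous label.

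The cost is one paragraph of analysis wording and one consistency check. No new data or visits are needed. What is given up is a durability claim against usual care, which the design cannot support.
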